2.8. Training process organization

2.8.1. Study staff training

Training of the Investigational Centers staff on the conduct of the study and the devices being used in the study will be performed before the protocol is implemented. All participating physicians, nurses and coordinators will be trained on the 780G system and the professional CGM. Specific Investigational

Center staff will be trained on each of the system's components. Training will contain both lecture and hands-on experience.

2.8.2. Patient training

At screening, all participants will be met by diabetes educator and dietitian to verify their knowledge related to intensive, functional insulin therapy. Patients not meeting the requirements will not be eligible to pursue the study.

The patients randomized to the AHCL group will be trained both in the field of technical aspect of the usage of this technology and clinical aspects of the 780G based diabetes management. The successful training will be confirmed with 780G system Training Checklist developed by investigator.

This training will include basics on insulin pump therapy, such as basal/bolus concepts, blood glucose target ranges, and insulin sensitivity; and basics on pump features, including how to program the pump, how to use the Bolus Wizard calculator, the importance of using the Bolus Wizard for all meals and correction doses, and the use of infusion sets and reservoir management. The training will also cover all the topics related to CGM usage.

A special attention will be accorded to the specific topics related to AHCL algorithm functioning, with "Let the algorithm work" treatment attitude.

3. EVENT DEFINITIONS AND REPORTING REQUIREMENTS DURING THE STUDY

Definitions:

Adverse Event (AE) (ISO14155-2) Any untoward medical occurrence in a subject An AE can, therefore, be any unfavorable and unintended sign (including an abnormal laboratory finding), symptom, or disease temporally associated with the use of a medicinal (investigational) product or medical device, whether or not related to the medicinal (investigational) product or medical device.

Serious Adverse Event (SAE) (ISO 14155-2) An adverse event that (a) Led to a death (b) Led to a serious deterioration in the health of the subject that • resulted in life threatening illness or injury, • resulted in a permanent impairment of a body structure or a body function • required in-patient hospitalization* or prolongation of existing hospitalization • resulted in medical or surgical intervention to prevent permanent impairment to a body structure or a body function (c) Led to fetal distress, fetal death or a congenital abnormality or birth defect *Inpatient Hospitalization is defined as: 24 hour acute admission to the hospital based on urgent medical need rather than elective admission. Note: A planned hospitalization for pre-existing condition, or a procedure required by the CIP, without a serious deterioration in health, is not considered to be a serious adverse event.

Serious Adverse Device Effect (SADE) (ISO 14155-2) Adverse device effect that has resulted in any of the consequences characteristic of a serious adverse event or that might have led to any of these consequences if suitable action had not been taken or intervention had not been made or if circumstances had been less opportune.

Unanticipated Adverse Device Effect (UADE) (21 CFR 812.3(s)) Any serious adverse effect on health or safety or any life-threatening problem or death caused by, or associated with, a device, if that effect, problem, or death was not previously identified in nature, severity, or degree of incidence in the investigational plan or application (including a supplementary plan or application), or any other unanticipated serious problem associated with a device that relates to the rights, safety, or welfare of subjects.

“Severe Hypoglycemia” is an event requiring assistance of another person to actively administer carbohydrate, glucagon, or other resuscitative actions. These episodes may be associated with sufficient neuroglycopenia to induce seizure or coma. Plasma glucose measurements may not be available during such an event, but neurological recovery attributable to the restoration of plasma glucose to normal is considered sufficient evidence that the event was induced by a low plasma glucose concentration. (American Diabetes Association Workgroup on Hypoglycemia, Diabetes Care 28:1245-1249, 2005)

“Severe Hyperglycemia” is defined as Hyperglycemia (blood glucose >270 mg/dL) with blood glucose ketones >0.6mmol/L or accompanied by symptoms of nausea, vomiting or abdominal pain.

“Diabetic Ketoacidosis/DKA” is defined as: Hyperglycemia (blood glucose >250 mg/dL or >13.9 mmol/L) with either low serum bicarbonate (<15 mEq/L) and/or low pH (<7.24) Anion gap (> 12) and either ketonemia or ketonuria and requiring treatment within a health-care facility. (American Diabetes Association-Diabetes Care, Volume 27, Supplement 1, January 2004).

The relatedness of the event to the study device or procedures will be determined for each adverse event.

The following definitions should be considered when determining the relationship of the event to the device or study procedure:

- Definite – clearly related to the device or procedure
- Probable – likely related to the device or procedure
- Possible – may be related to the device or procedure
- Unlikely – doubtfully related to the device or procedure
- Not Related – clearly not related to the device or procedure
- Unknown – not enough information exists to determine

Details of related adverse events, including episodes of severe hypoglycaemia, diabetic ketoacidosis, lipohypertrophy and injection/ infusion site infections, will be collected at each study visit and reported according to the requirements of the Bioethical Committee and to Medtronic. Adverse events will be captured by patients, carers and clinicians treating diabetes, and from interrogation of local hospital databases for details of hospital attendances.

4. AVOIDANCE OF BIAS

Participants will be randomised using a secure web-based randomisation programme. Participants will be randomised to each treatment arm in a 1:1 ratio. The randomisation code will be generated by a statistician using block randomisation with the random variable block size method.

Missing data will be monitored and strategies developed to minimise its occurrence; however, as much data as possible will be collected about the reasons for missing data and this will be used to inform the handling of missing data.

5. INFORMATION ABOUT QOL QUESTIONNAIRE

The following QOL questionnaire will be used: Speight J, Woodcock AJ, Reaney MD, Amiel SA, Johnson P, Parrott N, Rutter MK, Senior P, Smith R, Shaw JAM. The 'QoL-Q Diabetes' – a novel instrument to assess quality of life for adults with type 1 diabetes undergoing complex interventions including transplantation; presented at the Diabetes UK Professional Conference (Liverpool, UK: March 2010).

The questionnaire will be translated by study team under translation agreement along with Linguistic Validation Guidelines obtained from authors.

6. DATA HANDLING AND RECORD KEEPING

The investigator will retain all records and documents pertaining to this study. Data will be stored in a University Hospital in Krakow Data Archive Database. The Investigator will retain the source documents from which the information entered on the eCRF was derived. These records are to be retained in a secure storage facility maintained by the Investigational Center until 2 years after termination of the study. The Investigator should not dispose of these records without the approval of the Sponsor.

All data required for analysis will be captured on Case Report Forms (CRFs) developed by investigator. The Investigator will ensure that all CRFs are completed promptly, completely, and accurately. Information on case report forms will conform to the information in the source documents.

7. STATISTICS CONSIDERATIONS: SAMPLE SIZE CALCULATION AND STATISTICAL ANALYSIS

Statistical Hypothesis

The null-hypothesis $H_0: TIR_{MD/CSII} = TIR_{AHCL}$ will be tested against the alternative hypothesis $H_A: TIR_{MD/CSII} \neq TIR_{AHCL}$, where $TIR_{MD/CSII}$ and TIR_{AHCL} are the mean Time in Range (70–180 mg/dL) in the MDI/CSII and the AHCL groups, respectively.

Sample size

Using data from the study previously performed at our center a mean TIR=80% (Std=15%) in the AHCL group and a mean TIR= 65% (Std=15%) in the MDI/CSII group. For a two sided two-sample t-test, a total sample size of 40 subjects is required to test the hypothesized difference in population means of 15% with a 95% confidence level, 80% power and attrition rate of 15%.

Analysis of primary endpoint

The primary analysis will use a two-sample t-test to compare the mean TIR between the randomized arms of the study. The analysis will be adjust by baseline TIR. The mean TIR in the patients in the AHCL arm will be claimed to be smaller than then mean TIR in the MDI arm if the average TIR is smaller in the AHCL arm and the associated p-value of the test is less than 0.05. No extra adjustments are needed for this nested test.

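### The primary analysis is named as a two-sample t-test yet said to be adjusted for baseline TIR, so the deciding p-value is not tied to one test; name ANCOVA

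*Protocol*

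**What the plan says.** All the relevant text is in Protocol section 7.

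- Under the analysis of the primary endpoint: "The primary analysis will use a two-sample t-test to compare the mean TIR between the randomized arms of the study". The next sentence reads: "The analysis will be adjust by baseline TIR".
- The claim is made if the arm means differ in the stated direction and "the associated p-value of the test is less than 0.05".
- The sample size rests on the t-test without a covariate: "For a two sided two-sample t-test, a total sample size of 40 subjects is required". Its inputs are "a mean TIR=80% (Std=15%) in the AHCL group" and "a mean TIR= 65% (Std=15%) in the MDI/CSII group".

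The protocol names no ANCOVA, regression model or change score, and gives no correlation between baseline and final TIR. Section 2.7.1 provides for blinded CGM at baseline in every participant, so baseline TIR will be available in both arms.

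**The concern.** The two sentences on the primary analysis cannot both be carried out. A two-sample t-test compares two arm means and has no place for a covariate. Adjusting for baseline requires a different procedure, normally a linear model with arm and baseline TIR (ANCOVA), which has its own estimate, standard error and p-value. The claim rule refers to the p-value of the test without settling which test is meant.

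With about 17 evaluable participants per arm, a chance baseline imbalance or a useful baseline correlation can put the two p-values on opposite sides of 0.05. Staff and participants can see who has the pump system, so masking does not protect against choosing the method after the data are seen. Only a clear prior statement of the test does, and the current text is not one.

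**Working it through.** **Inputs.** From section 7: difference 80 − 65 = 15 points, SD 15 in both arms, two-sided alpha 0.05, 80% power, 15% attrition. From section 4: 1:1 allocation. Assumed, because the protocol does not give them: the correlation r between baseline and final TIR, and a baseline SD equal to the final SD.

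**1. The plan's own figure.** For a two-sample t-test with n per arm, the noncentrality is 15 / (15 × √(2/n)) on 2n − 2 degrees of freedom.

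- n = 16: power 78.1%.
- n = 17: noncentrality 1/√(2/17) = 2.915 on 32 df, power 80.7%.

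So 34 evaluable participants are needed, and 34 / (1 − 0.15) = 40. The stated 40 reproduces, and it belongs to the t-test without adjustment.

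**2. The adjusted analysis at the same size.** In ANCOVA the residual SD is 15 × √(1 − r²), and one further degree of freedom is used (31 df). The formula ignores chance imbalance in baseline TIR. The simulated column includes it (20,000 trials per row, 17 per arm, random baseline).

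**3. How often the verdicts differ.** Both tests were applied to the same simulated trials, with a true difference of 15 points. The last column is the share of trials in which one test was significant at 0.05 and the other was not.

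| Assumed r | Residual SD | Plain t-test power | ANCOVA power, formula | ANCOVA power, simulated | Tests disagree |
|---|---|---|---|---|---|
| 0 | 15.0 | 80.7% | 80.6% | 79.8% | about 4% |
| 0.3 | 14.3 | 80.7% | 84.1% | 83.1% | about 7-8% |
| 0.5 | 13.0 | 80.7% | 90.3% | 89.2% | about 12% |
| 0.7 | 10.7 | 80.7% | 97.7% | 97.3% | about 18% |

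By the formula, ANCOVA differs from the plain t-test by about 0, 3, 10 and 17 points of power as r rises from 0 to 0.7.

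**4. Sample size under ANCOVA.** For 80% power by the formula, with 15% attrition, the total is 40 at r = 0, 38 at r = 0.3, 31 at r = 0.5 and 24 at r = 0.7. The planned 40 is enough at each of these values.

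**The case against.** The strongest reply is that this is loose naming. The text plainly intends an adjustment, so an unadjusted primary test would contradict it. The natural reading is a comparison of means adjusted for baseline, and the exact model is commonly left to a statistical analysis plan, which is not at hand. Part of this stands: ANCOVA is the most sensible reading, and it is the one proposed below. But the protocol did not leave the model open. It named a test, and that test cannot do what the next sentence requires. An analysis plan that chose ANCOVA would depart from the named test, and one that chose the plain t-test would depart from the stated adjustment. Either way the protocol needs correcting.

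The objection is also right to limit the size of the point. A reader might infer any of the following, and the document does not support them:

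- **That the possible analyses differ very widely in power.** At low correlation, a wide gap appears only if a t-test on change from baseline is counted (67% power at r = 0.3, 52% at r = 0). Section 2.6 defines the primary endpoint, and section 7 the hypotheses, in terms of TIR itself and not its change. Where section 2.6 means baseline versus end of study, for vascular status, it says so. Between the plain t-test and ANCOVA the difference is negligible near r = 0.
- **That the trial is underpowered or the sample size wrong.** The 40 reproduces, and ANCOVA has about the planned power or more.
- **That the result would be biased.** Under randomisation both tests estimate the same mean difference. What is open is the choice of p-value.
- **That site must be added as a covariate or a particular month fixed as part of this repair.** Section 7 names only baseline TIR as an adjustment. The time point of the primary endpoint is a separate question.

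**Conclusion.** The point holds as a contradiction within section 7: the primary analysis cannot be carried out as written, and the p-value that decides the claim is not tied to one test. It should be corrected before any outcome data are examined.

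Its practical size depends on a correlation that the protocol does not give. Under the protocol's 15-point difference and SD of 15, with equal SDs at both times and 17 evaluable per arm, the plain t-test and ANCOVA reach opposite conclusions in about 4% of trials at r = 0, rising to about 18% at r = 0.7. ANCOVA gains nothing at r = 0, about 3 points of power at r = 0.3, and considerably more from r = 0.5 upward. The defect is an undefined test; neither the number of participants nor the data to be collected is called into question.

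**What to change.** Replace the two sentences on the primary analysis in section 7 with wording such as:

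> *The primary analysis is an ANCOVA of end-of-study TIR on treatment arm, with baseline blinded-CGM TIR as covariate, at a two-sided alpha of 0.05. The adjusted mean difference and its 95% confidence interval are reported. The unadjusted two-sample t-test is a sensitivity analysis.*

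The p-value in the claim rule should then be stated to be that of the treatment term in this model. The sample-size paragraph can stay as it is.

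The cost is two sentences and one degree of freedom. Baseline TIR is already collected in everyone, so no new data are needed. If baseline turns out to be uncorrelated with final TIR, the lost degree of freedom and chance baseline imbalance together cost about 1 point of power (80.7% against a simulated 79.8%).

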2.1. Objectives

The primary objective of this study is to evaluate whether the AHCL (MiniMed 780G®) system improves glycemic control and quality of life in older (above 65 years of age) individuals with T1D and if one year ACHL treatment may affect vascular improve of those patients.

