11. PRACTICAL VALUE AND FURTHER RESEARCH

We expect to see a significant improvement in both clinical outcomes and Quality of Life in patients who are naïve to pump and CGM technologies as they onboard on AHCL system. The consequence will be to broaden the population considered eligible to AHCL therapy and provide for the improvement of access.

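### The only directional claim rule for the primary endpoint is reversed: it covers AHCL having the smaller TIR, not the benefit the trial is planned to show

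*Protocol*

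**What the plan says.** Protocol section 7 sets a null hypothesis of equal mean TIR in the two arms against a two-sided alternative. The planning values are "Using data from the study previously performed at our center a mean TIR=80% (Std=15%) in the AHCL group" and 65% with the same SD in the MDI/CSII group. From these, "For a two sided two-sample t-test, a total sample size of 40 subjects is required", at 80% power and with 15% attrition.

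The analysis paragraph of the same section then states: "The primary analysis will use a two-sample t-test to compare the mean TIR between the randomized arms of the study". It continues: "The analysis will be adjust by baseline TIR". Next comes the claim rule: mean TIR on AHCL, it says, "will be claimed to be smaller than then mean TIR in the MDI arm if the average TIR is smaller in the AHCL arm", provided that the p-value is below 0.05. The paragraph ends: "No extra adjustments are needed for this nested test".

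Elsewhere the intended direction is clear. Section 2.1 asks whether the AHCL system "improves glycemic control and quality of life in older (above 65 years of age) individuals with T1D". Section 11 says: "We expect to see a significant improvement in both clinical outcomes and Quality of Life". Section 2.6 defines the primary endpoint only as a between-group difference in TIR, without a direction.

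**The concern.** TIR is the share of time with sensor glucose between 70 and 180 mg/dL, so a larger value is better; section 2.6 also counts participants above 70% TIR as a secondary endpoint. The claim rule says smaller twice, once in the claim and once in its condition. It therefore reads as a coherent rule for the wrong direction, not as a garbled word.

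The hypothesis itself is correctly two-sided, and a significant result with AHCL higher would reject it. The fault lies in the next step, which assigns a direction to the rejection. That step is written one way only, and it is the harmful way. The result the trial is planned to find is the one with no written claim rule. If the text stays as it is until results are known, the primary decision rule has to be corrected with the data in view, when it should have been fixed beforehand.

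A second, smaller fault sits in the same paragraph. A plain two-sample t-test of TIR does not adjust for baseline TIR. The rule refers to the p-value of the test, but two different analyses could supply it.

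**Working it through.** **Inputs (Protocol section 7; 1:1 allocation from section 4).** Means 80% and 65%, so δ = +15 points for AHCL; SD = 15 points in each arm; two-sided α = 0.05; power 80%; attrition 15%; total N = 40.

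**1. Reproduce the sample size.** For n evaluable patients per arm, the t statistic is noncentral t with df = 2n − 2 and noncentrality δ / (SD·√(2/n)).

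- n = 16: power 78.1%, too low.
- n = 17: df = 32, critical value 2.037, noncentrality 15 / (15·√(2/17)) = √8.5 = 2.915, power 80.7%.

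So 17 per arm, 34 in total, and 34 / 0.85 = 40. The stated N is reproduced exactly.

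**2. Split the rejection probability by direction (17 per arm).**

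| True difference | Noncentrality | P(significant, AHCL higher) | P(written rule met: significant, AHCL smaller) |
|---|---|---|---|
| +15 (planned) | 2.915 | 80.7% | 8.3e-7 |
| +10 | 10 / (15·√(2/17)) = 1.944 | 47.0% | 6.0e-5 |
| 0 | 0 | 2.5% | 2.5% |

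With all 40 patients evaluable (20 per arm) and the planned effect, the two probabilities are 86.9% and 2.3e-7.

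**3. Which observed results fall outside the rule.** At SD 15 and 17 per arm, the smallest significant observed difference is 2.037 × 15 × √(2/17) = 10.48 points. Any observed AHCL advantage of about 10.5 points or more rejects equality but meets no written claim rule.

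**4. Look for a rule elsewhere.** Section 2.1 states an aim, section 2.6 an undirected difference and section 11 an expectation. None says when AHCL may be claimed to be higher.

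**5. t-test against baseline-adjusted analysis.** The Protocol gives no correlation between baseline and end-of-study TIR, so a range was assumed. Trials were simulated (40,000 per setting) with 17 per arm, difference 15 and SD 15, comparing the plain t-test with an ANCOVA on baseline TIR. The two disagreed on whether there was a significant AHCL benefit in:

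- 9.6% of trials at correlation 0.4;
- 12.2% at 0.5;
- 15.0% at 0.6.

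A separate rerun gave about 9%, 12% and 15%. In that rerun most disagreements were ANCOVA significant and t-test not (7.2%, 10.7% and 13.8% of trials), against 2.2%, 1.7% and 1.1% the other way.

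**The case against.** The strongest reply is that this is a slip of wording with no statistical consequence. Rejecting a two-sided null and reading the sign of the estimate is the ordinary way to reach a directional conclusion. It needs no extra sentence and spends no extra alpha. On that view a significant AHCL advantage is interpretable from the Protocol as it stands, and no estimate, p-value or error rate changes. Much of this is right: the test, alpha and N are sound and the intended direction can be inferred. The 8.3e-7 is also not a loss of power. It is the small chance of a significant result against a treatment that is truly 15 points better, and it would be small under a correct plan too. What does not follow is that the sentence can stay. The Protocol chose to write a separate directional rule for its primary endpoint, and that rule contradicts the objective and the planning values in its own section.

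A second reply is that an SAP or amendment could correct the rule before analysis. It could, and correction after the results is then avoided. But this is not a detail left to the SAP; it is something the Protocol states wrongly, and a correct SAP would conflict with it until the Protocol is amended.

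On the t-test, it can fairly be said that adjustment for baseline is pre-specified and only the name of the test is loose. The disagreement rates rest on assumed correlations, and most of the disagreement is the expected gain in precision from adjusting. That keeps the point secondary, but the p-value that decides the primary claim still has two possible sources.

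**Conclusion.** The concern holds and should be fixed before analysis. The only directional claim rule for the primary endpoint is reversed, and no rule covers AHCL being higher. Under the Protocol's own assumptions (difference 15, SD 15, 17 evaluable per arm), 80.7% of trials would be significant with AHCL higher and practically none (8.3e-7) would satisfy the rule as written. This is an error in the decision rule only: the hypothesis, the two-sided 0.05 level and N = 40 stand.

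Reading the closing remark about a nested test as referring to this directional step is an interpretation, since the Protocol does not define the term; the conclusion does not depend on it.

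The mismatch between the t-test and the baseline adjustment is a secondary point. Its size, about 10% to 15% of trials with differing conclusions, depends on assumed correlations of 0.4 to 0.6.

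**What to change.** Replace the claim rule in section 7 with wording such as:

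> *AHCL will be claimed to give a higher mean TIR than MDI/CSII if the baseline-adjusted mean difference (AHCL minus MDI/CSII) is above 0 and the two-sided p-value is below 0.05.*

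A useful refinement is to add the mirror case (AHCL claimed lower if the difference is below 0 and p is below 0.05), so that the rule matches the two-sided hypothesis. Name the comparator MDI/CSII, as in the hypothesis, in place of MDI alone.

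In the same paragraph, replace the two-sample t-test with one named source of the primary p-value: ANCOVA of end-of-study TIR on arm and baseline TIR. Section 2.6 gives no time point for TIR; end of study fits the study-end CGM in section 2.7.2. The closing sentence on the nested test should be reworded to say plainly that reading the direction from the two-sided test needs no further alpha adjustment.

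The cost is one or two sentences of amended text. Alpha, sample size, data collection and patient procedures do not change.
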